5.2. Is there a sample size/power calculation?

No Yes: If yes; describe the calculation and the scientific rationale, and, if applicable, by site and key characteristics such as participant demographics

Intracluster correlation

The nature of the SCC program as a health system innovation precludes its randomization at the level of individual patients and instead incorporates a cluster design (i.e., randomization at the facility, or cluster, level). Estimating intracluster correlation coefficients (ICCs) is necessarily based on extrapolations from prior studies. ICC estimates have been derived for maternal and newborn health from the 2005 WHO Global Survey on Maternal and Perinatal Health (analyzing data from more than 90,000 pregnancies and births taking place in 120 hospitals in 8 Latin American countries). [22] For maternal and newborn outcome variables in this setting, the overall median ICCs were 0.011 (interquartile range 0.007–0.037) and 0.054 (interquartile range 0.013–0.075), respectively. Measures specific to this trial’s causal effect for which an ICC was estimated include neonatal death at 7 days (ICC=0.005) and maternal death (ICC=0.0003). The population studied and that in north India are not identical; clinical care delivered in Latin America may be of higher quality than that in UP; the implication is that ICCs may be lower in Latin America. For additional reference, numerous studies evaluating neonatal death in village settings in India and elsewhere in Asia use much lower ICCs, ranging from 0.0005 to 0.006. Considering these available data, and following discussion with biostatistics experts, including a reviewer at The Bill and Melinda Gates Foundation (BMGF), we therefore assume for this study the relatively conservative ICC estimate of ICC=0.01.

Cluster size and number

Clusters (i.e., facilities) of various sizes (i.e., annual birth volumes) will be enrolled in this trial. Public sector facilities to be included in the study are Primary health centers (PHCs), block PHCs, community health centers (CHCs), CHC/FRUs (First Referral Units), and District Women’s Hospitals (DWHs). UP has roughly 3,660 PHCs that vary widely in volume, from fewer than 150 deliveries annually to larger, so-called “block PHCs” (BPHC), that manage an average of 1,440 deliveries annually. These constitute a first “port of call” for a population of approximately 20,000-30,000 for most routine institutional deliveries with basic obstetric care. Each CHC acts as a referral center for 4-5 adjoining PHCs (on average) and provides specialist care including obstetrics and pediatrics to a population of 80,000 to 120,000. There are roughly 386 CHCs in UP and each has on average approximately 1,800 deliveries annually including a mix of referred and new cases. We therefore assume, for the sake of sample size calculations, that the expected average cluster size is 1,440 births (which is equal to the average annual birth rate of a BPHC), though we know that a minority subset of facilities will conduct less than 1,440 deliveries/year (e.g., small PHCs) and another minority subset of facilities will conduct more than 1,440 deliveries/year (e.g., CHCs). For operational reasons, we are only including facilities with more than 1,000 births/year by their report.

Matching effect

Matching will be conducted by exact matching on specified variables when possible and within bounded ranges of those variables when exact matching is not feasible. The matching process including matching variables is further discussed in the “methodology section” below.

Baseline event rate

The primary outcome in this trial is the rate of the composite measure of maternal death within 7 days, severe maternal complications within 7 days, fresh or macerated stillbirth, and neonatal death within 7 days.[18], [23] Taken together, data available from UP (described above in “Study Population”) suggest that the baseline rate of the primary outcome may be as high as 50-60/1,000 live births. Preliminary data from this study suggest that the baseline rate may actually be greater

than 100/1,000. The baseline rate used in this study will be 60/1,000; this is purposively set lower than the baseline data to (1) maintain conservatism since the preliminary data is based on a small sample and we do not want to risk under powering the study; and (2) to facilitate the possibility of demonstrating significant changes in sub-analyses (i.e., perinatal death rate).

Estimated event rate reduction

Based on knowledge of the relatively poor existing quality of healthcare services in UP, and the results of the SCC program pilot study which demonstrated marked improvement in health worker performance, we feel that achieving up to a 15% reduction in prior outcomes with the SCC program is feasible in this population and, at the same time, will enable the calculation of a practical sample size.

Statistical power

The Rao-Scott chi-square test statistic, which adjusts for the matched-pair cluster randomization scheme, will be used to compare the rates of the primary outcomes in the comparison and intervention groups. For our matched cluster randomized design, the necessary sample size per treatment group, N , using the Rao-Scott chi-square test statistic, can be written as a product of three terms:

$N = n \times Deff_C \times Deff_M$, where

n = sample size per treatment group for a simple random sample of independent patients

$Deff_C$ = Design effect 'for an unmatched cluster randomized design versus a simple random sample, $= 1 + (m-1) \times ICC$, with

m = average number of patients in a cluster (birth facility) ≈ 1440 patients

ICC = intra-cluster (birth facility) correlation coefficient $\approx .01$

$Deff_M$ = Design effect 'for a matched versus unmatched cluster randomized design

In this study, with $ICC=0.01$, we approximate $Deff_C = 15.4$, so that within-facility clustering has a significant impact. The best available estimate for $Deff_M$ when using our matching algorithm can be obtained from our team member's matched cluster randomized design in Mexico.[41, 47] In the Mexico study (in which 14 outcomes were measured), $Deff_M$ was at most 0.55 (resulting in at least a 45% reduction in the total sample size); 10 outcomes had a $Deff_M$ of 0.2 or smaller (giving at least an 80% reduction in the total sample size); and 7 outcomes had a $Deff_M$ of 0.1 or smaller.

Because our major constraint is the number of facilities that can be enrolled in the trial, and not the number of patients per facility (since we will be able to measure all patients in a facility on the main outcomes), the total number of patients per treatment group in the sample size calculation above (N) is mainly relevant in that it determines the required number of facilities. The total number of facilities equals 2 times the total number of patients per group divided by the expected cluster size:

$$\text{Total number of clusters} = 2 \times N / m$$

We assume that matching will have some effect but do not want to risk overestimating that effect, and will therefore incorporate the smallest matching effect in the sample size calculations. The result (using an $ICC=0.01$ and a matching design effect of 0.55) is a trial enrolling 120 facilities (60 pairs of facilities) for a total of 171,964 births (86,000 births in each arm) that will detect a 15% reduction in the primary outcome from 60/1,000 to 51/1,000 live births with 80% power and an alpha value of 0.05. However, we will have 80% power to detect a smaller reduction in the primary outcome, if the matching effect is ultimately stronger than this conservative estimate.

6. Recruitment Methods

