4.4. List inclusion criteria

For measuring outcomes, we will include all mothers admitted to a study site for childbirth, excluding those who have been referred into the facility by an inter-facility transfer, those being managed for abortion and those who refuse. In case a mother or baby from an enrolled site is referred out to another facility (before or after delivery) the mother-baby dyad will be included in the study and the outcome will be allocated to the referring facility.

For a smaller subset of pause-points during birth events (as detailed above), health worker practices will be directly observed to measure the impact of the SCC program on delivery of essential practices, as a secondary outcome. A convenience sample of women and babies cared for by the health workers around the time of childbirth at the facility during data collectors' duty hours will be included in this component of the study.

Site recruitment

Due to the nature of the program the unit of intervention will be at the facility level. Hence, the recruitment plan will include selecting health facilities conducting deliveries and enrolling them into either the intervention or comparison arms.

Each of the six regions will contribute approximately 20 facilities (approximately 10 each in intervention and comparison arms) leading to a total of 120 facilities. Sites will be spread across districts in each region and will be matched-paired across districts.

Site identification

Study sites will be identified, vetted, and enrolled using a predefined structured selection process. Eligibility criteria include: geographic location of the facility within study districts; facility being a PHC, BPHC, CHC, CHC/FRU or DWH; willingness of the facility leaders and staff to participate in the study; facility being a 24X7 functional National Rural Health Mission (NRHM) accredited birth center; having at least three birth attendant trained at the Auxiliary Nurse Midwife (ANM) level or above; a birth volume of at least 1,000 births annually; willingness to

provide its newborn and maternal outcome data; and having no potentially confounding ongoing research or quality improvement programs at the time of selection.

Site enrollment

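### The stated 80% power assumes facilities of equal size; it is about 79% to 77% if the CV of facility size is about 0.2 to 0.3 (assumed), and it depends on a closure rule that the plan states in two ways

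*Combined protocol and SAP*

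**What the plan says.** Section 5.2 (Statistical power) builds the sample size as N = n × Deff_C × Deff_M per arm, with Deff_C = 1 + (m − 1) × ICC and m the average number of births per facility. With ICC 0.01, m about 1,440 and Deff_M 0.55, it concludes that 60 pairs and 171,964 births "will detect a 15% reduction in the primary outcome from 60/1,000 to 51/1,000 live births with 80% power and an alpha value of 0.05". It adds that N "is mainly relevant in that it determines the required number of facilities".

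The same section says "Clusters (i.e., facilities) of various sizes (i.e., annual birth volumes) will be enrolled in this trial", with minorities of facilities below and above 1,440 deliveries a year. Of CHCs it says "each has on average approximately 1,800 deliveries annually". Section 4.4 requires "a birth volume of at least 1,000 births annually". District Women's Hospitals are also eligible, but no volume is given for them. No CV or size distribution appears anywhere.

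On the analysis, Section 5.2 says "The Rao-Scott chi-square test statistic, which adjusts for the matched-pair cluster randomization scheme, will be used to compare the rates", without naming facility weights. Section 2.2 (Primary outcome) defines the rate relative to the total number of birth events.

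On closure, Section 4.2 has up to 18 months per facility and a stop once 171,964 birth events are reached. Section 4.4 has up to 18 months after the last site is enrolled. On enrolment, Section 4.2 gives 15 months in the text and month 40 in the table (16 months after month 24), while Section 4.4 gives about 20 months.

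**The concern.** When facilities contribute different numbers of births and each birth counts once, large facilities carry extra weight and the variance of the arm-level rate rises. The usual allowance replaces m by (1 + CV²)m in Deff_C. The plan acknowledges unequal sizes but leaves this term out. Matching on birth volume, which Section 4.4 lists as a candidate, makes sizes alike within a pair, not across pairs.

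The closure rule bears on the same quantity. What matters is births observed per facility, which is volume multiplied by observation time. If pairs start months apart and all stop together, early pairs contribute more births even at identical volumes.

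At stake is the accuracy of one stated number. A null result would be read against 80% power, and that number has no allowance for a feature the plan itself describes.

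**Working it through.** **Inputs.** From Section 5.2: rates 0.060 and 0.051, α = 0.05 (taken as two-sided, the only reading that reproduces the target), power 80%, ICC 0.01, m = 1,440, Deff_M 0.55, 120 facilities, 171,964 births. The CV of facility size is not given and is assumed below.

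**Step 1: reproduce the plan.** The pooled two-proportion formula gives n = 10,158 per arm. Deff_C = 1 + 1,439 × 0.01 = 15.39. Then 10,158 × 15.39 × 0.55 = 85,982 per arm, and twice the unrounded value is 171,964.8, the stated total. Dividing by 1,440 gives 119.4 facilities, rounded up to 120. The target is exactly the equal-size formula, and the only slack is that rounding.

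**Step 2: add the size term.** Power = Φ(0.009 / √(v × Deff_C × 0.55 / 85,982) − 1.96), where
- v = 0.06 × 0.94 + 0.051 × 0.949 = 0.1048;
- Deff_C = 1 + [(1 + CV²)m − 1] × 0.01;
- m = 171,964 / 120 = 1,433.

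| CV of births per facility (assumed) | Deff_C | Power, births-weighted |
|---|---|---|
| 0 | 15.32 | 80.2% |
| 0.18 | 15.78 | 79.0% |
| 0.20 | 15.89 | 78.7% |
| 0.30 | 16.61 | 76.9% |
| 0.31 | 16.70 | 76.7% |

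For CV 0.20, for example, the standard error is √(0.1048 × 15.89 × 0.55 / 85,982) = 0.00326; 0.009 / 0.00326 = 2.757; Φ(2.757 − 1.96) = 78.7%. If the matching gain is applied only to the between-facility part of the variance, the results barely change: 79.1% at CV 0.18 and 76.9% at 0.31.

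**Step 3: is a CV of 0.2 to 0.3 plausible?** Mixing the documents' own volumes of 1,000, 1,440 and 1,800 in assumed shares of 20/60/20, 25/50/25 or one third each gives CVs of 0.18, 0.20 and 0.23, and power of 79.0%, 78.7% and 78.2%. A right-skewed distribution with floor 1,000 and mean 1,440 gives 0.31; its shape is assumed. The upper end of the range is therefore less well anchored than the lower.

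**Step 4: a common stop at 171,964 births.** Assume 120 births per facility-month everywhere (1,440 / 12) and an 18-month cap.
- First 15 pairs starting in months 0–3, the other 45 over months 8–16, 12–16 or 15–20: CV about 0.31 to 0.34, power about 76% to 77%.
- All 60 pairs enrolled evenly over 15, 16 or 20 months: CV about 0.35 to 0.43, power about 74% to 76%.

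These figures contain no volume variation. Volume variation would add to the loss.

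**Step 5: how much the conservative inputs give back.** At CV 0.31:
- Deff_M of 0.507 instead of 0.55, or a baseline of 64.8 per 1,000 with the same 15% reduction, restores 80%.
- A baseline of 100 per 1,000 gives 94%.
- Deff_M of 0.2 gives 99%.

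**The case against.** The strongest reply is that the effect lies within planning noise. The ICC is extrapolated from other settings: at equal sizes, an ICC of 0.009 gives 83.9% and 0.011 gives 76.6%, so a change of 0.001 matters more than the whole size correction. The baseline was deliberately set below preliminary data exceeding 100 per 1,000. Deff_M of 0.55 is the least favourable of 14 outcomes in the earlier matched trial, and 10 of those were 0.2 or smaller. All of this stands, and it is why the point is minor. It offsets the omission without correcting it: Section 5.2 presents a stronger matching effect as extra sensitivity, not as cover for unequal sizes.

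A reader might go further in four ways that the documents do not support.
- *The trial is underpowered.* Step 5 of the working shows that modest departures from the conservative inputs more than restore 80%.
- *The loss follows from the plan's own inputs.* It does not, because the plan gives no CV.
- *The weighting is open.* No weights are written down, but a test on a rate per birth event is births-weighted unless other weights are declared. Facility weights would keep about 80% but would estimate something other than that rate.
- *There is a 12-month closure rule.* Sections 4.7 and 9.1 only time a survey at about 12 months, near the end of a site's outcome collection.

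There is also a fair objection to Step 4. It has the first 15 pairs supplying about 36% to 38% of births. Section 5.1 expects about 45,000 births at the interim, when Phase II data collection is described as complete, and 45,000 / 171,964 is about 26%. The 74% to 77% range is therefore conditional on reading the Section 4.2 stop literally.

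**Conclusion.** The point holds as a minor error. The 171,964 births and 80% power are exact only for facilities of equal size, which the plan says it will not have. For the births-weighted rate, with 60 against 51 per 1,000, ICC 0.01, Deff_M 0.55 and 120 facilities, power is about 79% to 77% if the size CV is about 0.2 to 0.3. Under a common stop with staggered enrolment it is about 74% to 77%, given assumed enrolment dates and equal monthly volumes.

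The CV and the enrolment dates are assumptions; the missing term is not. The conflict between the closure and enrolment statements is also plain from the text. At its limits, Section 4.4 allows 20 + 18 = 38 months, beyond the trial phase of up to 36 months in Section 4.2 and the final analysis at up to 35 months in Section 5.1. Actual power may still exceed 80%.

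**What to change.** 1. Compute Deff_C as 1 + [(1 + CV²)m − 1] × ICC, with the CV taken from the birth volumes already gathered for eligibility and matching, and restate the power in Section 5.2.
2. State in Section 5.1 that the Rao-Scott comparison is births-weighted, consistent with the per-birth-event rate in Section 2.2.
3. Reconcile the closure statements in Sections 4.2 and 4.4 and the three enrolment statements (15 months, month 40, about 20 months). Base the restated power on births expected per facility under the reconciled rule, so that unequal observation time is included.

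The cost is one recalculation and a few sentences, with no added facilities. The downside is a stated power a few points lower. The restatement can say alongside it that the baseline rate and matching effect were chosen conservatively.

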6.1. Does the study involve the recruitment of participants?

No: If no, skip to 7.1

Yes: If yes; indicate how, when, where, and by whom participants will be recruited

Please see Section 4.7 as well as Section 9.1 for detailed information on our recruitment.

6.2. Are there any materials that will be used to recruit participants, e.g., emails, posters, and scripts?

No **Yes: If yes; provide a list of the materials (also include copies with the application)**

7. Available Resources

7.1. Describe the feasibility of recruiting the required number of participants within the recruitment period

BetterBirth sites have been selected in accordance with a minimum average delivery load of 1,000 deliveries per year and data collection period scheduled accordingly. Based on what BetterBirth has observed to date, consent refusal and lost to follow up cases have been minimal. Therefore, BetterBirth does not anticipate any challenges in recruiting the required number of participants within the recruitment period.

7.2. Describe how the Principal Investigator will ensure that a sufficient amount of time will be devoted to conducting and completing the research

The senior PI devotes 15% of his time to this project. Additionally, the BetterBirth director and co-PI is working full-time on this project.

7.3. Are there research staff members, in addition to the Principal Investigator?

No:

Yes: If yes; outline training plans to ensure that research staff members are adequately informed about the protocol and study-related duties

In Boston, about 20 individuals support BetterBirth research and have been trained on our protocol and study design.

In India, there are over 250 research staff members on the ground; all have received extensive study-related training. One module of their training is specifically devoted to understanding the BetterBirth study design; separate modules of training focus on consent processes and ethics.

7.4. Describe the minimum qualifications for each research role (e.g., RN, social worker) their experience in conducting research, and their knowledge of local study sites and culture

Those doing direct observation (FADAs and FADA TLs), as well as our program coaches, typically have a nursing background. Field-based data collectors and call-center operators generally have previous on-the-ground program implementation or research experience.

7.5. Briefly describe how the research facilities and equipment at the research site(s) support the protocol's aims, e.g., private rooms available for interviews, etc.

The study has two major areas of data collection. One is observation of essential birth practices, which takes place in the admission, labor/delivery, and discharge rooms in accordance with the design of the WHO Safe Childbirth Checklist.

Data on outcomes will be collected from the BetterBirth call center allowing the participant to answer questions about maternal and neonatal mortality and morbidity from the privacy of their home.

7.6. Are there provisions for medical and/or psychological support resources (e.g., in the event of incidental findings, research-related stress)?

No Yes: **If yes; describe the provisions and their availability**

8. Vulnerable Populations

8.1. Are there any potentially vulnerable populations (e.g., children, pregnant women, human fetuses, neonates, prisoners, elderly, economically disadvantaged, employees or students of the investigator or sponsor, undocumented, terminally ill, cognitively impaired or mentally ill, etc.)?

No: **If no, skip to 9.1**

Yes: **If yes; identify all vulnerable populations**

Vulnerable populations include pregnant women and their neonates.

8.2. Describe safeguards to protect their rights and welfare

Please see Risk (section 10) and Participant Privacy (section 14) below.

9. Consent Process

9.1. Will consent to participate be obtained?

No: **If no, skip to 9.5**

Yes: **If yes; describe the setting, role of individuals involved, timeframe(s), and steps to minimize coercion/undue influence during the consent process (at the time of initial consent and throughout the study)**

The study is of a quality improvement intervention designed to improve the delivery of essential birth practices as defined by the national guidelines. The risk of the proposed data collection is minimal and so informed consent procedures are designed to reflect this low risk and to not increase risk for any participants.

In our BetterBirth Protocol, surrogate consent refers to consent that is given by a family member (such as the husband, mother, or mother-in-law) in the case that a woman is unable to consent for herself.

There are two situations where surrogate consent is used, namely: (1) at the time of labor and delivery for observation of care provided by birth attendant; and (2) at discharge/referral out for follow-up of the mother-infant pair. At observation, surrogate consent is taken if the woman is in advanced labor and cannot carry a conversation. At discharge or referral out, the defined scenarios in which we consider a woman unable to consent for herself include when (1) the mother has died at the facility; (2) when the woman is referred out and unable to consent for herself as she is too ill; or (3) when the woman is unable to consent for herself (i.e. unable to carry out a conversation), but not referred out.

Facility and HCW

Agreement for participation including randomization of facilities in the each district will be obtained from the District Chief Medical Officer (CMO). He will be asked to provide a letter of support and agreement for the district to participate and to endeavor to obtain essential supplies. Agreement will also be obtained from the facility Medical Officer in Charge (MOIC) for participation of the facility in the study. The staff will be oriented to the study and study procedures by the study team leader and an informational sheet shared tailored to whether the site is a control or intervention facility. (See HCW Info Sheet Intervention and Control)

